3.1 Statistical Analysis Plan

3.1.1 Primary Analyses

Incidence of maternal death or sepsis and intrapartum/neonatal death or sepsis will be compared between the two treatment arms using generalized linear models. These generalized linear models will be fit with each binary outcome separately as the outcome measure. Estimates of relative risk and associated 95% confidence intervals will be reported. The model will include terms for treatment and site. As randomization occurs at the pregnancy level and approximately 1-2% of pregnancies are anticipated to be multiple gestations, models for neonatal outcomes will account for correlation among multiples assuming an exchangeable covariance structure. For the two primary outcomes, these analyses will be conducted using the ITT population and the p-values associated with the treatment term will be used to formally test each of the two primary hypotheses at the alpha = 0.05 level.

As secondary analyses of the primary outcomes, assuming an overall treatment effect is observed, the models will be run including region (Africa, Latin America, or Asia) and a treatment by region interaction

term. If the interaction term has a $p < 0.1$, then effects will be reported by region with treatment effect within region tested at the 0.025 level.

Additional exploratory models will also be run including individually: 1) a treatment by site interaction term, 2) any other antibiotic use during labor (yes or no) and its interaction with treatment, and 3) mode of delivery (cesarean or vaginal) and its interaction with treatment. If the interaction term for any of these models has a $p < 0.1$, then effects will also be reported by the relevant subgroups. These exploratory secondary models will also include any demographic or clinical variables found to differ significantly between the treatment arms in the preliminary analyses described above.

From each final model, estimates of relative risk associated with treatment will be obtained including unadjusted estimates of risk from the primary model as well as estimates of risk adjusted for potential confounders from the secondary analyses.

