Given the above information, we propose a sample size of 34,000 participants for the overall study. For the primary neonatal outcome of interest of intrapartum/neonatal sepsis or death, assuming that the loss to follow-up will be in the 2% to 3% range (consistent with the current ASPIRIN trial and the Global Network Maternal and Newborn Health registry), this sample size will be sufficient to provide 90% power to detect a 25% reduction in neonatal mortality and sepsis in the sub-Saharan African region and will provide 90% power to detect a 20% reduction in Asia assuming the baseline risk is at least 8%. For the primary maternal outcome of maternal death or sepsis, the sample size will provide 90% power to detect a 20% reduction from 3% in the population aggregated across all study sites.

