The sample sizes shown above assume that the hypothesis test of interest is for the overall population and that the Type 1 error is controlled at the neonatal and maternal hypothesis level via testing each at an alpha = 0.05 level. Interest has been expressed for the overall study for being able to test the neonatal risk separately in south Asia and sub-Saharan Africa. Controlling the Type I error rate at the 0.025 level for each of those two areas within this sub-analysis of neonatal risk will be conducted to avoid multiple comparison concerns. The resulting sample sizes for that comparison are shown in Table 2 below. Note that this sample size would be the size required separately for the African and Asian sites. It is planned that each site will enroll approximately equal number of participants. As such, approximately 37.5% of randomized mothers will be from sub-Saharan Africa and 50% will be from Asia. This planned enrollment distribution is approximately equivalent to the rates of in-facility deliveries observed in the GN registry database. Specifically, approximately a third of the facility deliveries are conducted in sub-Saharan Africa and between 45% and 50% of the facility deliveries are conducted in Asia. These estimates are also consistent with the enrollment rates for the ASPIRIN study that is currently being conducted at these sites. Therefore, to get the total study sample size required, the numbers in the table would need to be multiplied by 3 to achieve reasonable power for the African sites.

Table 2. Sample Sizes Within Region, Alpha=0.025

Baseline risk	Risk Reduction	Evaluable Sample Size per Arm		
		Power=0.80	Power=0.85	Power=0.90
8%	20%	4961	5607	6477
8%	25%	3093	3496	4038
8%	30%	2091	2363	2729

14%	20%	2669	3017	3485
14%	25%	1677	1884	2176
14%	30%	1129	1276	1474

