Given the above information, we propose a sample size of 34,000 participants for the overall study. For the primary neonatal outcome of interest of intrapartum/neonatal sepsis or death, assuming that the loss to follow-up will be in the 2% to 3% range (consistent with the current ASPIRIN trial and the Global Network Maternal and Newborn Health registry), this sample size will be sufficient to provide 90% power to detect a 25% reduction in neonatal mortality and sepsis in the sub-Saharan African region and will provide 90% power to detect a 20% reduction in Asia assuming the baseline risk is at least 8%. For the primary maternal outcome of maternal death or sepsis, the sample size will provide 90% power to detect a 20% reduction from 3% in the population aggregated across all study sites.

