7.5 Multiple Comparisons and Multiplicity

There is one formal hypothesis test for each of the maternal and neonatal population of the study. Each population will be analyzed and interpreted separately and thus analyses are not adjusted for multiplicity between these populations. The statistical test of the primary outcome in each population will be conducted at an overall 5% type I error rate (two-sided) with p-value allocation between the interim and final analyses as detailed in Section 11.

The study sample size was determined to provide sufficient power to test for treatment effects within the high-risk cohort as the main secondary aim and also within region. As these are secondary aims, no adjustment multiplicity was applied to the planned primary study analyses. However, to avoid over-interpretation of regional findings the sub-analysis of the primary neonatal outcome within the Asian and African regions will be conducted controlling the Type I error rate at the 0.025 level.

However, all other analyses of secondary outcomes are exploratory in nature; therefore, p-values and confidence intervals are provided for descriptive purposes only. Additionally all p-values provided for any baseline and demographic characteristics and safety parameters will be for descriptive purposes only. As such, unless otherwise specified, p-values presented will be on a per analysis basis, with no further control for multiple tests.

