9.3 Primary Analysis

The primary outcomes of incidence of maternal death or sepsis and incidence of intrapartum/neonatal death or sepsis will be compared between the two treatment arms using generalized linear models. These generalized linear models will be fit with each binary outcome separately as the outcome measure. Estimates of relative risk and associated 95% confidence intervals will be reported. The model will include terms for treatment and site. As randomization occurs at the pregnancy level and approximately 1-2% of pregnancies are anticipated to be multiple gestations, models for neonatal outcomes will account for correlation among multiples assuming an exchangeable covariance structure. If a model for neonatal outcomes has convergence issues, then the generalized linear model will be fit without the adjustment for correlation among multiples. For the two primary outcomes, these analyses will be conducted using the ITT population and the p-values associated with the treatment term will be used to formally test each of the two primary hypotheses at the alpha = 0.05 level.

The primary analyses using the ITT population will use multiple imputation for missing outcomes implemented separately for mothers vs. infants via logistic regression imputation using site and high-risk status prior to randomization as covariates. As sensitivity analyses, the primary outcomes will also be analyzed without imputation for individuals in the ITT population, without imputation for individuals in the per-protocol population; and in the ITT population assuming all missing outcomes are sepsis or death as well as assuming all missing outcomes are not sepsis nor death.

As secondary analyses of the primary outcomes, the models will be run including region (Africa, Latin America, or Asia) and a treatment by region interaction term. If the interaction term has a $p<0.1$, then effect estimates and associated confidence intervals will be reported by region with treatment effect within region for Africa and Asia tested at the 0.025 level.

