9.5 Secondary Outcome Analyses

Binary secondary outcomes (e.g. individual components of the primary outcome, all other infection indicators, use of antibiotics, maternal and neonatal readmission as well as admission special care unit, maternal GI symptoms, and pyloric stenosis) will be analyzed in a similar manner to the primary analysis of the primary outcomes. Models will be focused on providing estimates of relative risk and associated confidence intervals as opposed to being used for formal tests of hypothesis. If regional differences are observed for the primary outcome, then region-specific models for all secondary outcomes will be run in order to get region-specific estimates of relative risk.

For secondary publications, secondary outcomes may also be explored using additional exploratory models including individually: 1) a treatment by site interaction term, 2) any other antibiotic use during labor (yes or no) and its interaction with treatment, and 3) mode of delivery (cesarean or vaginal) and its interaction with treatment. If the interaction term for any of these models has a $p < 0.1$, then effects will also be reported by the relevant subgroups. These exploratory secondary models will also include any demographic or clinical variables found to differ significantly between the treatment arms in the preliminary analyses described above. From each final model, adjusted relative risk estimates for treatment will be obtained.

For the outcome of time from drug administration until initial discharge after delivery and the outcome of neonatal initial hospital length of stay, the same analysis steps will be employed but using models appropriate for the distribution of these variables (Brock 2011). Specifically, Kaplan-Meier survival curves will be fit to the data in order to get cumulative incidence curves by treatment group of hospital discharge, obtained by treating in-hospital mortality as a competing risk.

10. SAFETY ANALYSIS:

No formal safety analyses are planned as a part of this study, although SAEs and side effects will be summarized. No formal hypothesis tests will be conducted, but descriptive p-values generated using Cochran-Mantel-Haenszel statistics with stratification by GN site will be generated.

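### The Africa and Asia neonatal tests depend on interaction p<0.1 in SAP 9.3, but SAP 7.5 and the 90% regional power claims carry no such condition and are not met under it when regional effects are similar

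*Combined protocol and SAP*

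**What the plan says.** **Conditional text.** SAP 9.3 fits a model with region (Africa, Latin America, Asia) and its interaction with treatment, and continues: "If the interaction term has a $p<0.1$, then effect estimates and associated confidence intervals will be reported by region", with Africa and Asia tested at 0.025. Protocol 3.1.1 has the same p<0.1 condition and a further one: "As secondary analyses of the primary outcomes, assuming an overall treatment effect is observed, the models will be run including region". SAP 9.3 drops that further condition, and SAP section 12, as provided, records no change. SAP 9.5 follows similar logic for secondary outcomes: "If regional differences are observed for the primary outcome, then region-specific models for all secondary outcomes will be run".

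**Text with no condition.** SAP 7.5 describes the planned enrolment as "determined to provide sufficient power to test for treatment effects within the high-risk cohort as the main secondary aim and also within region", and adds that "the sub-analysis of the primary neonatal outcome within the Asian and African regions will be conducted controlling the Type I error rate" at 0.025. SAP 6.1 gives the purpose as "being able to test the neonatal risk separately in south Asia and sub-Saharan Africa", sets out Table 2 at alpha 0.025, and states that 34,000 women "will be sufficient to provide 90% power to detect a 25% reduction in neonatal mortality and sepsis in the sub-Saharan African region", with 90% power for a 20% reduction in Asia, at a baseline risk of at least 8%. Protocol 3.2.1 makes the same claims. None of these passages mentions an interaction test.

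**The concern.** The two sets of text can be read in two ways, and each leaves a fault. If SAP 7.5 means that the regional neonatal tests are always done, it contradicts SAP 9.3. If SAP 7.5 sets only the alpha level and SAP 9.3 sets the condition, the 90% power belongs to a procedure that is not the planned one.

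An interaction test seldom reaches p<0.1 when the drug works about equally well everywhere. In that case the regional relative risks, their confidence intervals and the two tests would usually not be reported, although the sample size text leads a reader to expect them at 90% power. If the choice of rule is left until after unmasking, it can depend on the results.

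The point concerns the neonatal outcome only, since SAP 7.5 and Table 2 do.

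**Working it through.** **Inputs from the documents.** 34,000 women, 1:1 allocation; Africa 37.5% and Asia 50% of enrolment; 2-3% loss; two-sided 0.025 per region; interaction threshold 0.10; baseline risk 8% to 14%; reductions of 25% (Africa) and 20% (Asia).

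**Assumptions not in the documents.** Latin America has the remaining 12.5% (one of eight sites). Its true effect is varied. One baseline risk applies to all three regions unless stated. One infant per woman; site terms and imputation are left out.

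**Step 1: reproduce Table 2.** With pooled variance,

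n per arm = [z(α/2)·√(2p̄(1−p̄)) + z(β)·√(p₀(1−p₀) + p₁(1−p₁))]² / (p₀−p₁)²

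with z(α/2) = 2.2414 and z(β) = 1.2816.

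- Africa, p₀ = 0.08, p₁ = 0.06: (2.2414·√0.1302 + 1.2816·√0.1300)² / 0.02² = 4,038.
- Asia, p₀ = 0.08, p₁ = 0.064: (2.2414·√0.133632 + 1.2816·√0.133504)² / 0.016² = 6,477.

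Both match the printed 90% figures, and nothing in the formula involves an interaction test.

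**Step 2: power without the condition.** Evaluable per arm at 3% loss:

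- Africa: 34,000 × 0.375 / 2 × 0.97 = 6,184
- Asia: 34,000 × 0.5 / 2 × 0.97 = 8,245
- Latin America: 34,000 × 0.125 / 2 × 0.97 = 2,061

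Power is 98% in Africa and 96% in Asia, so the 90% claim is true for an unconditional test.

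**Step 3: an upper bound with the condition.** Conditional power = P(interaction p<0.1 and regional test significant) ≤ P(interaction p<0.1). If the true relative risks are equal, that probability is 0.10. The bound depends on neither the baseline risk nor Latin America's share, and more women would not raise it.

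**Step 4: simulation with the condition.** 400,000 trials per scenario: binomial counts, regional log relative risks with Wald variances, a 2-df heterogeneity test at 0.10, and regional tests at two-sided 0.025.

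| True reduction Africa / Asia / Latin America | Baseline | P(interaction p<0.1) | Power, lower to higher of the two regions |
|---|---|---|---|
| 25 / 25 / 25% | 8% | 0.10 | 9-10% |
| 20 / 20 / 20% | 8% | 0.10 | 7-9% |
| 25 / 20 / 20-25% | 8% | 0.17 | 14-17% |
| 25 / 20 / 15% or 30% | 8% | 0.23-0.25 | 20-24% |
| 25 / 20 / 40% | 8% | 0.59 | 55-58% |
| 25 / 20 / 0% | 8% | 0.66 | 62-65% |
| 25 / 20 / 20-25% | 14% | 0.23-0.24 | 22-24% |
| 25 / 20 / 40% | 14% | 0.83 | 83% |
| 25 / 20 / 0% | 14% | 0.89 | 89% |

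With Africa and Asia at 8% but Latin America at 14%, Africa/Asia power is about 83%/81% if Latin America has no effect and 77%/74% if its reduction is 40%. With Latin America at 20-25% it stays at 14-18%.

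**Step 5: strongly differing effects, 8% baseline.** If only Africa benefits (25%), conditional power for Africa is 94%. If only Asia benefits (20%), it is 82% for Asia. With protocol 3.1.1's overall-effect requirement added, these fall to 67% and 64%.

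**Step 6: selection.** With Africa 25%, Asia 20% and Latin America 20-25% at an 8% baseline, the true Africa-to-Asia ratio of relative risks is 0.94. Its geometric mean is 0.94 over all trials but 0.86 over trials where interaction p<0.1, so the contrast is exaggerated when it is reported.

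**The case against.** The strongest reply is that the plan is coherent. SAP 9.3 is the operative analysis section and agrees with protocol 3.1.1 on the p<0.1 condition. SAP 7.5 only fixes the alpha, to prevent over-reading of regions, which the condition also does. Secondary aim h asks whether the effect differs by region, and the interaction test answers that; no listed aim asks for separate regional efficacy. Table 2 is an ordinary two-proportion calculation and is correct as such.

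Much of this stands. The condition looks deliberate, it is a reasonable safeguard, and Table 2 is not wrong. But on this reading the power paragraphs still describe a test that the plan would usually not carry out when effects are similar, so they need correcting.

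The practical loss is also limited. In the similar-effect cases the pooled neonatal test has over 99.9% power. SAP 9.1 summarises data by arm and region in any case, so crude relative risks can be calculated, and SAP 7.4 provides a descriptive look at sites. The maternal outcome alone needs about 2 × 15,334 / 0.97 = 31,600 women, so the trial size does not rest on the regional claim.

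It is also fair that the figures with a very different Latin America effect move with its assumed baseline risk, as Step 4 shows. The 10% bound does not move, and the 14-17% result barely does.

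**Conclusion.** The point holds. Whether the Africa and Asia neonatal tests are conditional is stated inconsistently, and the 90% regional power is true only if they are not. Under SAP 9.3 as written, that power is at most about 10% when relative effects are equal. It is 14-17% at the plan's own effects with an 8% baseline and a 20-25% reduction assumed in Latin America (22-24% at a 14% baseline). With one baseline for all regions and Latin America's reduction varied from 0 to 40%, neither region reaches 90%: the range is 14-65% at 8% and 22-89% at 14%. Among the strongly differing cases run, Africa passes 90% if it alone benefits (94%), while Asia does not if it alone benefits (82%). Beyond the 10% bound, the figures rest on assumed regional effects and baselines. Reading the SAP 9.3 sentence as reporting regional results only if p<0.1 is its natural sense, though the word *only* is not there. What is at stake is the separate regional neonatal estimates and tests, not the two primary conclusions.

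**What to change.** Reconcile the passages before unmasking, by one of two routes.

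(a) **Unconditional.** For the primary neonatal outcome, amend SAP 9.3 and protocol 3.1.1 so that the Africa and Asia relative risks are always reported and each is tested at 0.025, with confidence intervals matched to that level. Give the interaction p-value beside them as the evidence on aim h. This delivers what SAP 7.5 and the sample size text describe. It adds two regional estimates to the report, and the 0.025 level already covers the two tests.

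(b) **Conditional.** Keep SAP 9.3, add the p<0.1 condition to SAP 7.5, and state in SAP 6.1 and protocol 3.2.1 that the 90% regional power is for an unconditional test and does not hold for the conditional procedure when regional effects are similar. This keeps the guard against over-reading regions and gives up the regional power claim.

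Under either route, say whether protocol 3.1.1's overall-effect requirement applies, and record any departure from the protocol in SAP section 12.

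No women or data are added. A change to the protocol text may need submission to the ethics committees, as its recent versions did. If that is unwelcome, a clarification in the SAP, recorded in section 12, would settle the rule.

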- h. To determine whether the effect on each of the primary outcomes differs by region (Africa, Latin America or Asia), any other antibiotic use during labor, and mode of delivery (cesarean or vaginal). Note that antibiotic use will not include use to treat any infections diagnosed after randomization as those will be outcomes.

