2.2.2 Exclusion Criteria

- Non-emancipated minors (as per local regulations)
- Evidence of chorioamnionitis or other infection requiring antibiotic therapy at time of eligibility (however, women given single prophylactic antibiotics with no plans to continue after delivery should not be excluded).
- Arrhythmia or known history of cardiomyopathy.
- Allergy to azithromycin or other macrolides that is self-reported or documented in the medical record.
- Any use of azithromycin, erythromycin, or other macrolide in the 3 days or less prior to randomization.
- Plan for cesarean delivery prior to randomization.
- Preterm labor undergoing management with no immediate plan to proceed to delivery.
- Advanced stage of labor (>6 cm or 10 cm cervical dilation per local standards) and pushing **or** too distressed to understand, confirm, or give informed consent **regardless** of cervical dilation.
- Are not capable of giving consent due to other health problems such as obstetric emergencies (for example, antepartum haemorrhage) or mental disorder.
- Any other medical conditions that may be considered a contraindication per the judgment of the site investigator.
- Previous randomization in the trial.

Sites may choose to obtain written consent during antenatal care from pregnant women of the age of consent who plan to deliver vaginally in a facility and have no known medical exclusions. In this case, study staff must fully assess and confirm eligibility at the time of randomization. It may also be necessary to verbally re-confirm consent at the time of randomization, if required by local regulations. If it is determined that the study needs to be extended to accrue the planned sample size for HR cohort, then women who deliver prior to meeting HR criteria for randomization will be excluded.

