4.1 Data Forms

The following forms will be used for this study:

Form Name	Purpose	Key Data Elements	Data Source
Contact and Scheduling Form	To facilitate participant follow-up by documenting contact information and projected study visit schedule	Contact information, date of enrollment, date of follow-up visits	Participant interview, study calendar
Screening and Enrollment Form	To determine eligibility and record consent status	Screening date, review and confirmation of inclusion/exclusion criteria, consent status/date.	Participant interview/report, clinical assessment, provider report, medical records
Randomization Form	To confirm eligibility and track randomization	Eligibility confirmation, randomization date/time, drug administration date/time, any problems with drug administration (e.g., vomiting, dropped med, etc).	Study records, participant interview and observation

Form Name	Purpose	Key Data Elements	Data Source
Maternal Baseline Data Form	To collect additional maternal information	
 Demographic and baseline clinical data: admission date/time, EDD, GA, age, height, weight, pregnancy and medical history, etc. Events during labor and delivery: timing of onset of labor, prolonged labor, premature rupture of membranes, date/time/type of membrane rupture, date/time/type of delivery, indication for induction (if applicable), vital signs during labor (temp, HR, RR, BP), complications, etc. Events after delivery: complications, vital signs, etc. Infection assessment pre- and post-delivery Antibiotic treatment pre- and post-delivery Discharge information 	Participant interview/report, provider report, medical records
Neonatal Baseline Data Form	To collect information about the infant directly after delivery.	
 Sex Birthweight Delivery outcome (live or stillbirth) Complications Infection assessment Discharge information: date/time, status (discharged, transferred, died) 	Participant interview/report, provider report, medical records
Maternal and Neonatal Follow-up Form	To collect maternal and infant health status during follow-up visits at 3 days, 7 days and 42 days after delivery.	
 Timing follow-up Maternal and infant status since discharge: general status, symptoms, indication of infection, clinic visits, hospitalizations, antibiotic use Temperature 	In-person participant interview/report and clinical exam

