For secondary publications, additional exploratory models will also be run including individually: 1) a treatment by site interaction term, 2) any other antibiotic use during labor (yes or no) and its interaction with treatment, and 3) mode of delivery (cesarean or vaginal) and its interaction with treatment. If the interaction term for any of these models has a $p<0.1$, then effects will also be reported by the relevant subgroups. These exploratory secondary models will also include any demographic or clinical variables found to differ significantly between the treatment arms in the preliminary analyses described above. From each final model, adjusted relative risk estimates for treatment will be obtained. Kaplan-Meier survival curves will be fit to the data in order to get cumulative incidence curves by treatment group of the timing of the first occurrence of maternal death or sepsis and intrapartum/neonatal death or sepsis.

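### Mode of delivery, and to a lesser degree other antibiotic use in labor, arise after randomization, so the treatment interactions planned for aim 1.3h can reflect selection rather than effect modification

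*Combined protocol and SAP*

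**What the plan says.** Aim h in protocol 1.3, repeated in SAP 3.2, asks whether the effect on each primary outcome differs by region, by other antibiotic use in labor and by mode of delivery. Protocol 3.1.1 and SAP 9.3 implement the last two as separate models, one with "any other antibiotic use during labor (yes or no) and its interaction with treatment" and one with "mode of delivery (cesarean or vaginal) and its interaction with treatment". If an interaction has p<0.1, "then effects will also be reported by the relevant subgroups". SAP 9.5 allows the same models for secondary outcomes. SAP 9.3 calls them exploratory and assigns them to secondary publications.

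Four other places matter:

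- Protocol 2.2.2 excludes women with a "Plan for cesarean delivery prior to randomization".
- The same section says that "women given single prophylactic antibiotics with no plans to continue after delivery should not be excluded", so some labor antibiotics precede randomization.
- Aim h adds a limit: "Note that antibiotic use will not include use to treat any infections diagnosed after randomization as those will be outcomes".
- The maternal baseline form in protocol 4.1 lists "Antibiotic treatment pre- and post-delivery", that is, timing relative to delivery and not to randomization.

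SAP 9.2 defines neither modifier as an analysis variable.

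**The concern.** A subgroup comparison keeps the protection of randomization only if treatment cannot influence who is in the subgroup. Mode of delivery does not meet that condition by design: with planned cesarean excluded, the decision comes after randomization. If azithromycin prevented some of the fevers or suspected infections that lead to cesarean, the cesarean group in the azithromycin arm would lose some of its highest-risk women to the vaginal group. The cesarean relative risk would look better than the truth and the vaginal one worse, with no real difference in effect.

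The outcome can also come first. Maternal sepsis counts if it occurs in labor after randomization (protocol 2.5), and the neonatal composite includes intrapartum loss after randomization (SAP 9.2). Either may influence how the woman delivers.

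The antibiotic modifier has the same structure, but the limit in aim h removes the most obvious route. Other use after randomization still counts, such as prophylaxis or treatment without a diagnosed infection.

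At stake is the answer to a stated secondary aim. A reader of subgroup relative risks triggered by a small interaction p-value would naturally take them as effect modification.

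**Working it through.** **The plan's own figure first.** Table 1 gives 15,334 per arm for the maternal outcome (3% versus 2.4%, two-sided 0.05, 90% power). With the pooled-variance formula:

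n = [1.960·√(2·0.027·0.973) + 1.2816·√(0.03·0.97 + 0.024·0.976)]² / 0.006² = 15,334 after rounding up.

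It reproduces. The documents give no figure for the interaction tests beyond the 0.1 threshold.

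**Inputs from the documents.** Total 34,000 women with 2% to 3% loss. At 2.5%, that is 34,000 × 0.975 / 2 = 16,575 evaluable per arm. Baseline risk is 3% maternal and 8% neonatal (the low end of 8% to 14%). Protocol 1.4.2 puts the cesarean rate at 5% to 10% or lower, especially in the Africa region, and says cesarean raises maternal infection risk by up to 5 to 10 times.

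**Assumptions (not in the documents).** The true relative risk is 0.80 for every woman. One tenth of women carry a 12% maternal risk and nine tenths carry 2%: 0.1 × 0.12 + 0.9 × 0.02 = 3.0%. Placebo cesarean rates are 30% and 8%: 0.1 × 0.30 + 0.9 × 0.08 = 10.2% overall. Azithromycin lowers cesarean only in the high-risk tenth, to 28.5%, 27% or 24%.

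**Worked case, 30% to 24%.**

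- Cesarean, placebo: (0.1·0.30·0.12 + 0.9·0.08·0.02) / 0.102 = 0.00504 / 0.102 = 4.94%.
- Cesarean, azithromycin: 0.8·(0.1·0.24·0.12 + 0.9·0.08·0.02) / 0.096 = 0.8·0.00432 / 0.096 = 3.60%. Relative risk 0.73.
- Vaginal, placebo: (0.030 − 0.00504) / 0.898 = 2.78%.
- Vaginal, azithromycin: 0.8·(0.030 − 0.00432) / 0.904 = 2.27%. Relative risk 0.82.
- Ratio of relative risks: 0.89, although the true ratio is 1.

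**Chance of p<0.1.** I used a Wald test of the log ratio of relative risks, ignoring the site term. The variance is the sum over the four arm-by-mode cells of (1 − risk) / events. Expected events are 83.5 and 57.3 (cesarean, placebo and azithromycin) and 413.7 and 340.5 (vaginal), so the standard error is 0.183. With ln 0.891 = −0.115, the standardized shift is 0.63, and P = Φ(−1.645 + 0.63) + Φ(−1.645 − 0.63) = 0.17.

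For the neonatal outcome I multiplied both risks by 8/3 to reach 8% and ignored multiple births. The relative risks do not change, but events rise by 8/3 and the standard error in the last row falls to 0.108.

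| Cesarean in high-risk tenth | Overall, placebo vs azithromycin | RR cesarean / vaginal | P(p<0.1) maternal | P(p<0.1) neonatal |
|---|---|---|---|---|
| 30% in both arms | 10.2% vs 10.2% | 0.80 / 0.80 | 0.10 | 0.10 |
| 30% to 28.5% | 10.2% vs 10.05% | 0.78 / 0.80 | 0.10 | 0.11 |
| 30% to 27% | 10.2% vs 9.9% | 0.77 / 0.81 | 0.12 | 0.15 |
| 30% to 24% | 10.2% vs 9.6% | 0.73 / 0.82 | 0.17 | 0.28 |

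With all cesarean rates scaled to 5% overall, the last row's maternal figure falls to 0.13. A separate simulation with a latent risk factor (600 replicates) gave 0.17 maternal and 0.27 neonatal at 10.2% versus 9.5%. At 10.2% versus 8.7%, a larger shift than any in the table, it gave 0.30 and 0.65.

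**The case against.** The strongest reply is that the bias depends on an effect nobody has shown. The documents report no effect of azithromycin on cesarean. The US trial enrolled women already undergoing cesarean, infection needing treatment is excluded at entry, and some sites may enroll up to 10 cm dilation, which probably leaves little time to alter the decision. That stands: with no shift, and no outcome preceding delivery, the test keeps its 10% rate. A reader might infer that these interaction tests will show false differences; the documents support only that they can.

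Second, aim h already removes antibiotics given for infections diagnosed after randomization. This also stands and answers much of the antibiotic half. A reader might infer that the antibiotic subgroup is defined by treatment of the outcome itself, but the text rules that out for diagnosed infections. What remains is other use after randomization, and the removal is itself a classification made after randomization.

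Third, the models are exploratory and kept for secondary publications. That limits the harm, but the label does not tell a reader that the subgroups are non-randomized. The plan recognizes this kind of problem elsewhere: protocol 3.1.2 and SAP 9.4 plan a sensitivity analysis for women who become high-risk after randomization, because that status is a post-randomization event. Nothing similar is planned here.

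**Conclusion.** The point holds as a modest one. Mode of delivery is a post-randomization variable that the outcome can precede, so its treatment interaction and the subgroup relative risks have no clear causal reading. Labor antibiotic use has the same weakness to a lesser degree. Region is fixed at baseline, so it would be wrong to read the whole of aim h as compromised.

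Over the assumed shifts in the table, the spurious gap runs from 0.78 versus 0.80 to 0.73 versus 0.82. The maternal false-signal rate rises from 0.10 to at most about 0.17 and the neonatal rate to about 0.28. These figures rest on the assumed risk strata, cesarean rates and shifts. No figure was worked out for the antibiotic modifier. The primary tests, their alpha and the sample size are unaffected.

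**What to change.** In SAP 9.3 and 9.5:

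- Report mode of delivery and other antibiotic use in labor by arm, so readers can see whether either was shifted.
- Label results within mode of delivery as descriptive and non-randomized.
- If the mode-of-delivery interaction is kept, add a sensitivity analysis like the one in SAP 9.4: test for an arm difference in the modifier and, if there is one, estimate how far it could move the subgroup effects. Dropping the interaction altogether is defensible but not required, since it belongs to a stated aim.
- Define the antibiotic modifier in SAP 9.2 as use before randomization, if recorded timing allows. The form list gives randomization date and time but places antibiotics only before or after delivery, so the data coordinating center should confirm this first. If the timing cannot be separated, give that subgroup the same non-randomized label.

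The cost is SAP wording and a little more analysis. The antibiotic subgroup would be smaller, and the claim that can be made for aim h weaker.
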